5.2.12 ADVS - Vital Signs Analysis

The ADVS contains data on vital sign assessments for all randomised subjects. Converted assessments are also included in this dataset for a list of vital sign assessments which have been reported in multiple units, see Appendix C.

The ADVS is built in two steps and based on the SDTM datasets VS, XV, SUPPVS, and information from ADBR. The first step builds the complete ADVS without the core efficacy and

Statistical Program. Specification		Date:	10 September 2019	Novo Nordisk
Trial ID: NN2211-4232	CONFIDENTIAL	Version:	1.0	
UTN: U1111-1170-7035	CONFIDENTIAL	Status:	Final	
EudraCT No: 2015-002417-29		Page:	34 of 42	

safety baseline variables. The second step depends on the completed ADSL dataset and adds the efficacy and safety core baseline variables.

BMI on CRF is excluded from ADVS and replaced by derived BMI. The BMI is derived at all control visits with topic code (topic_cd = "BMI_DERIVED") and DTYPE is set to "DERIVED" and where the record is set to ANELFL = "Y".

Note, that are no entries for investigator comments on the vital sign CRF forms, and therefore no ACOMNT variable included in ADVS data.

5.2.13 ADTTE – Time-to-Event Analyses

. The ADTTE contains data on time-to-event corresponding to primary and secondary endpoints.

The variables ALBNDDT and ARBNDDT are defined in section 3.6.12.

If an event is met, then the CNSR (censoring) is assigned as 0 else 1.

5.2.14 ADRESP – Responder Analysis

ADRESP contains the dichotomous endpoints calculated from observed data in ADHBA1C without any imputations.

TOPIC_CD	PARAM	PARAMCD
HBA1C_BLOOD_65	HbA1c <=6.5% (IDF)	HBA_BL65
HBA1C_BLOOD_LE70_WO_WEIGHT_		HLE7WOW
GAIN	HbA1c <=7% without weight gain	G
HBA1C_BLOOD_LE70_WO_TE_SEV_	HbA1c <=7% without treatment	HLE7WOH
BG_HYPO	emergent sever hypoglycaemic	Y
	episodes or blood glucose confirmed	
	symptomatic hypoglycaemic	
	episodes	
HBA1C_BLOOD_LE70_WO_WEIGHT_	HbA1c <=7% without weight gain	HLE7WOW
GAIN_TE_SEV_BG_HYPO	and no treatment emergent severe	Н
	hypoglycaemic episodes or blood	
	glucose confirmed symptomatic	
	hypoglycaemic episodes	

Table 16Parameters included in ADRESP dataset

Statistical Program. Specification Trial ID: NN2211-4232 UTN: U1111-1170-7035 EudraCT No: 2015-002417-29	CONFIDENTIAL	Date: Version: Status: Page:	10 September 2019 1.0 Final 35 of 42	Novo Nordisk

These endpoints will be derived using the last post-baseline measurements of HbA1c on treatment, last measurement of body weight taken on treatment, baseline body weight and the hypoglycaemic episodes in period from TRTSDT till Analysis Date.

AVALC will be derived as "Y" or "N" based on the criteria for each topic_cd.

CONFIDENTIAL

Date: Version: Status: Page:

6 Data conformance summary

This section will be updated in the Analysis Data Reviewers Guide.

CONFIDENTIAL

Date: Version: Status: Page:

7 Submission of Programs

This section will be updated in the Analysis Data Reviewers Guide.

CONFIDENTIAL

Date: Version: Status: Page:

8 Specification of output

See PSPS version 1.0.

CONFIDENTIAL

Date: Version: Status: Page:

9 References

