The purpose of the MMRM analysis is to estimate the treatment effects that would have been observed if all subjects had remained on treatment and completed all visits, instead of dropping out. The analysis relies on the assumption that data are missing at random (MAR), which means that given the observed data, the events that lead to data being missing are independent of the unobserved data. This is a reasonable assumption also for subjects discontinuing treatment due to inadequate glycaemic control since it can be explained by the observed data obtained prior to discontinuation.

Categorical endpoints related to HbA1c

Secondary categorical efficacy endpoints are subjects who at 104 weeks or at premature treatment discontinuation achieve (Yes/No):

Protocol Trial ID: NN2211-4232 UTN: U1111-1170-7035 Evdrec T as : 2015 002417 20	CONFIDENTIAL	Date: Version: Status:	04 September 2015 1.0 Final	Novo Nordisk
EudraCT no.: 2015-002417-29		Page:	51 of 67	

- $HbA_{1c} \leq 6.5\%$
- $HbA_{1c} \le 7.0\%$ without weight gain
- $HbA_{1c} \le 7.0\%$ without treatment emergent severe hypoglycaemic episodes or BG confirmed symptomatic hypoglycaemic episodes
- $HbA_{1c} \le 7.0\%$ without weight gain and no treatment emergent severe hypoglycaemic episodes or BG confirmed symptomatic hypoglycaemic episodes

These endpoints will be analysed separately using the same type of logistic regression model. In the calculation of the responses, the last post-baseline measurements of HbA_{1c} and body weight which were taken on treatment will be used. The model will include treatment arm as a factor and baseline HbA_{1c} as a covariate. The results will be described by the odds ratio for the comparison of Victoza[®] versus OAD and the associated 95% confidence interval and two-sided p-value.

Other efficacy endpoints

The change from baseline at 104 weeks or at premature treatment discontinuation will be evaluated for:

- FPG
- Body weight
- BMI
- Systolic and diastolic blood pressure

These endpoints will be analysed using the same type of ANCOVA as for HbA_{1c} but with the baseline measurement of the corresponding endpoint as covariate instead of baseline HbA_{1c} . The corresponding supportive analyses to estimate treatment differences at different visits will also be performed.

BMI will be derived at each visit with a body weight measurement by using the body weight from the corresponding visit and the height measured at screening.

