Treatment emergent: hypoglycaemic episodes will be defined as treatment emergent if the onset of the episode occurs on or after the first day of trial product administration, and no later than the day after the last day of trial product administration.

Protocol		Date:	04 September 2015	Novo Nordisk
Trial ID: NN2211-4232	CONFIDENTIAL	Version:	1.0	
UTN: U1111-1170-7035	CONFIDENTIAL	Status:	Final	
EudraCT no.: 2015-002417-29		Page:	53 of 67	

Nocturnal hypoglycaemic episodes: are episodes occurring between 00:01 and 05.59 both inclusive.

[figure not shown]
Hypoglycaemic episodes are classified according to the Novo Nordisk classification of hypoglycaemia (see Figure 17–2) and the ADA classification of hypoglycaemia (see Figure 17–3).

Novo Nordisk classification of hypoglycaemia

In normal physiology, symptoms of hypoglycaemia occur below a plasma glucose level of 3.1 mmol/L (56 mg/dL).²¹ Therefore, Novo Nordisk has included hypoglycaemia with plasma glucose levels below this cut-off point in the definition of blood glucose (BG) confirmed hypoglycaemia.

Novo Nordisk uses the following classification (see Figure 17–2) in addition to the ADA classification:

- Severe hypoglycaemia according to the ADA classification $\frac{22}{2}$.
- Symptomatic BG confirmed hypoglycaemia: An episode that is BG confirmed by plasma glucose value < 3.1 mmol/L (56 mg/dL) with symptoms consistent with hypoglycaemia.
- Asymptomatic BG confirmed hypoglycaemia: An episode that is BG confirmed by plasma glucose value < 3.1 mmol/L (56 mg/dL) **without** symptoms consistent with hypoglycaemia.
- Severe or BG confirmed symptomatic hypoglycaemia: An episode that is severe according to the ADA classification²² or BG confirmed by a plasma glucose value < 3.1 mmol/L (56 mg/dL) with symptoms consistent with hypoglycaemia.
- BG confirmed hypoglycaemia: An episode that is BG confirmed by a plasma glucose value < 3.1 mmol/L (56 mg/dL) with or without symptoms consistent with hypoglycaemia.
- Severe or BG confirmed hypoglycaemia: An episode that is severe according to the ADA classification²² or BG confirmed by a plasma glucose value < 3.1 mmol/L (56 mg/dL) with or without symptoms consistent with hypoglycaemia.

[figure not shown]

Note: Glucose measurements are performed with capillary blood calibrated to plasma equivalent glucose values

Figure 17–2 Novo Nordisk classification of hypoglycaemia

ADA classification²² of hypoglycaemia

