2.3.3 On-treatment period

In accordance with protocol on-treatment definition as follows: the on-treatment period is defined as the observations occurring from when subject initiates randomised treatment (treatment start date) to

- Efficacy parameters, safety lab and hypos: 1 day after last dose of randomised treatment (both days included)
- AEs: 7 days after last dose of randomised treatment (both days included)

For missing date of last dose see section 3.6.1.

For subjects in the safety analysis set (SAFFL = "Y"), the baseline assessments (ABLFL = "Y") in the in-trial period (INTRFL = "Y") will be included in the on-treatment period (ONTRTFL = "Y").

The variable ONTRTFL are used to define periods on-treatment. ONTRTFL will be 'Y' for all records in the period on-treatment and 'N' at other periods. The ONTRTFL will be included in all datasets with visit structure (BDS).

3 Analysis considerations related to multiple analysis datasets

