3.6.5 Treatment emergent events

A Treatment Emergent Adverse Event (TEAE) is defined as an event with onset or increase in severity on or after the time of first trial product administration and no later than seven days (7 times 24 hours) after the time of last trial product administration.

A Treatment Emergent hypoglycaemic episode is defined as an event with onset on or after the time of first trial product administration and no later than one day (24 hours) after the time of last trial product administration.

If the date and datetime of the event is not missing or is partial, the exact number of hours since trial product administration is used to determine if the event is treatment emergent. This also means that an event on the same date as trial product administration will not be treatment emergent if the time of the event is before time of trial product administration.

However, if the start-date and datetime for the adverse event or hypoglycaemic episode is missing or partial, and an imputed date or datetime can result in an onset of the event that is within the treatment emergent period, then the event is defined as treatment emergent. Otherwise it is defined as non-treatment emergent. Following partial date and datetime rules should be applied:

- If the time of the event is partially observed such that only the hours are observed, the event is regarded as treatment emergent if the date and hour of the event is the same as for the trial product administration or if the treatment-emergent window extends to at least the beginning of the given hour.
- If the time (hours) of the event is missing the event is regarded as treatment emergent if it occurs on the date of trial product administration or no later than the specified amount of time after this date.
- If date is missing or partial missing the event is not regarded as treatment emergent.

Statistical Program. Specification		Date:	10 September 2019	Novo Nordisk
Trial ID: NN2211-4232	CONFIDENTIAL	Version:	1.0	
UTN: U1111-1170-7035	CONFIDENTIAL	Status:	Final	
EudraCT No: 2015-002417-29		Page:	19 of 42	

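### SAP 5.2.14 counts hypoglycaemia for two responder endpoints only to an undefined Analysis Date, not to the end of the treatment-emergent window

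*SAP*

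**What the plan says.** Protocol 17.4.1.1 lists four categorical HbA1c endpoints. Two involve hypoglycaemia: HbA1c at or below 7.0% "without treatment emergent severe hypoglycaemic episodes or BG confirmed symptomatic hypoglycaemic episodes", and the same with no weight gain added. For the calculation, the last post-baseline HbA1c and "body weight which were taken on treatment will be used". That sentence sets no cut-off for hypoglycaemia.

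The cut-off comes from the definition of treatment emergent. Protocol 17.4.1.2 takes episodes with onset from the first dosing day and "no later than the day after the last day of trial product administration". SAP 3.6.5 says much the same: "no later than one day (24 hours) after the time of last trial product administration".

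SAP 5.2.14 describes the responder dataset. It states that "ADRESP contains the dichotomous endpoints calculated from observed data in ADHBA1C without any imputations", and that "These endpoints will be derived using the last post-baseline measurements of HbA1c on treatment", together with the last on-treatment weight, the baseline weight and "hypoglycaemic episodes in period from TRTSDT till Analysis Date". Table 16 still labels both endpoints as treatment emergent. For the hypoglycaemia count endpoints, SAP 5.2.9 (Table 15) selects episodes by the treatment-emergent flag, TRTEMFL.

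**The concern.** The label and the derivation in SAP 5.2.14 use different windows. If Analysis Date is the date of the last on-treatment HbA1c, a subject can have a severe or BG-confirmed symptomatic episode while still taking trial product and be reported as having reached target without hypoglycaemia. The same episode would enter the event-rate analysis through Table 15, so two outputs of one trial could disagree about one subject.

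The subjects exposed are those who stop early. An episode that contributes to stopping tends to fall after the last scheduled HbA1c, which is the part of follow-up the rule may leave out.

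**Working it through.** The plan states no figure on this point, so there is none to reproduce. The check compares the texts and then sizes the gap.

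**1. The windows**

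| Source | Start | End |
|---|---|---|
| Protocol 17.4.1.2 | first dosing day | day after last dosing day |
| SAP 3.6.5 | first dose | 24 hours after last dose |
| SAP 5.2.9, Table 15 | TRTEMFL | TRTEMFL |
| SAP 5.2.14 | TRTSDT | Analysis Date (undefined) |

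**2. What Analysis Date can mean.** The responder records come from the HbA1c dataset and use the last on-treatment HbA1c, so the date of that record is the natural reading. It remains an inference. If the last weight date was meant, the mismatch with last dose remains. If treatment end was meant, the SAP already has TRTEDT for that and does not use it here.

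**3. Direction of the error.** Under SAP 2.3.3 an on-treatment HbA1c can be dated no later than one day after last dose. On the natural reading the 5.2.14 window therefore lies inside the treatment-emergent window. It can omit episodes but cannot add any, so responder counts can only rise.

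**4. Length of the gap.** HbA1c is taken at weeks 16, 26, 38, 52, 65, 78, 91 and 104 (protocol flow chart; SAP 3.6.12.1). Successive gaps are 10, 12, 14, 13, 13, 13 and 13 weeks, or 70, 84, 98, 91, 91, 91 and 91 days. The longest is weeks 38 to 52: 14 × 7 = 98 days nominal, and 98 + 10 + 10 = 118 days at the edges of the visit windows. For a completer with an on-treatment week 104 sample, the gap is about 0 to 1 day.

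**5. Who is exposed.** A subject must stop between visits, have a last on-treatment HbA1c at or below 7.0%, and have no withdrawal sample within one day of last dose. For example: HbA1c at or below 7.0% at week 38, an episode and last dose at week 45, and the withdrawal sample taken more than one day later. The week 38 value is then the last on treatment, the 5.2.14 window closes at week 38, and the subject is a responder. Table 15 counts the episode.

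**6. Chance of an omitted episode.** The documents give no hypoglycaemia rate. I assume 0.1 to 1 episode per year, a constant rate, and stopping spread evenly over a 13-week interval, which gives a mean gap of 13/2 = 6.5 weeks. P = 1 − exp(−rate × gap).

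- Mean gap, 0.1 per year: 1 − exp(−0.1 × 6.5/52) = 1.2%
- Mean gap, 1 per year: 1 − exp(−1 × 6.5/52) = 11.8%
- 98-day gap, 0.1 per year: 1 − exp(−0.1 × 98/365.25) = 2.6%
- 98-day gap, 1 per year: 1 − exp(−1 × 98/365.25) = 23.5%

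A constant rate understates the chance for subjects whose stopping was prompted by an episode.

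**7. Scale for an arm.** Protocol Amendment 1 (change to 17.1) expects 200 subjects per arm, of 1994/2 = 997, to stop without inadequate control. If all 200 were exposed at the mean gap, 200 × 1.2% ≈ 2.5 to 200 × 11.8% ≈ 23.5 subjects would be misclassified, or 0.25 to 2.4 percentage points of the arm. This overstates the number exposed: some will have a usable withdrawal sample, and those who stop before week 16 generally have no post-baseline HbA1c.

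**The case against.** The strongest reply is that the SAP never says counting stops at the HbA1c date. SAP 1.1 presents the document as deviations from and additions to a project-level specification, and refers also to define.xml. Neither is available here, and Analysis Date may be defined in one of them. That stands as a caution. What the documents do show is an undefined cut-off that differs from the wording of the endpoint.

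The gap also closes for some subjects. Protocol 8.1.5 asks for visit 12 procedures as soon as possible after withdrawal, and these include HbA1c. If that sample falls within one day of last dose, it is on treatment and an earlier triggering episode is counted. A reader might infer that episodes leading to discontinuation are almost always missed; the documents do not support that.

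A reader might also infer that the rule favours the arm with more hypoglycaemia. That depends on rates, stopping times, HbA1c at the last visit and completeness of withdrawal samples by arm, and the documents settle none of these.

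Finally, simply substituting TRTEMFL is not a clean repair. SAP 5.2.8 describes the flag as the on-treatment period plus one more day, while SAP 2.3.3 already ends that period for hypoglycaemia one day after last dose. Read literally, the flag runs to two days after last dose. SAP 3.6.6 (Table 9) instead ends the on-treatment period at TRTEDT, which would give one day. Table 8 takes TRTEDT as the earliest of several dates, including the last on-treatment visit. If that applies beyond missing dates, and the flag is built on TRTEDT, the substitution could recover almost none of the gap. This objection stands and shapes the fix.

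**Conclusion.** The point holds as a mismatch between the SAP derivation and the endpoint it is meant to implement. On the natural reading of Analysis Date, up to about 14 weeks of treatment-emergent time is uncounted for early stoppers with HbA1c at or below 7.0% and no sample within one day of last dose, and the error can only inflate responder counts. About 1% to 12% of such subjects would be misclassified, conditional on the assumed rates and mean gap. The effect on the treatment comparison cannot be given a size or a sign.

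The reach is narrow. Only two of the four responder endpoints are involved, and protocol 4.2.2.1 marks neither as key. Completers are essentially unaffected, and subjects whose last on-treatment HbA1c exceeds 7.0% are non-responders either way. The primary endpoint does not use this rule, and the hypoglycaemia counts have their own. This is a minor correction that is worth making.

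**What to change.** In SAP 5.2.14, replace the Analysis Date cut-off with the treatment-emergent window of SAP 3.6.5 and protocol 17.4.1.2: episodes with onset from first dose to one day after the actual last dose. If an earlier cut-off is intended, define Analysis Date and justify the departure from the protocol.

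Reconcile the TRTEMFL description in SAP 5.2.8 with sections 2.3.3 and 3.6.5 so that the flag does not add a second day. State whether the Table 8 rule for TRTEDT applies only when the last-dose date is missing.

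The cost is a sentence in 5.2.14 and a clarification in each of two other places. The dates and episodes are already collected, so no new data are needed.

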Appendix A Table shells location

Table 17Table shells location

Document	novoDOCS object ID
4232-sec-14-1-demographic-data-statistical-table-shells	
4232-sec-14-2-efficacy-data-statistical-table-shells	
4232-sec-14-3-1-adverse-events-statistical-table-shells	
4232-sec-14-3-2-deaths-saes-statistical-table-shells	
4232-sec-14-3-4-abnormal-lab-list-statistical-table-shells	Not Applicable
4232-sec-14-3-5-lab-displays-statistical-table-shells	
4232-sec-14-3-6-other-safety-observations-displays-statistical-	
table-shells	
4232-sec-14-3-7-other-safety-observations-lists-statistical-table-	Not Applicable
shells	
4232-sec-16-2-1-discontinued-patients-statistical-table-shells	
4232-sec-16-2-3-patients-excluded-from-efficacy-analysis-	Not Applicable
statistical-table-shells	
4232-sec-16-2-4-individual-demographic-data-statistical-table-	
shells	
4232-sec-16-2-5-compliance-and-drug-concentration-data-	Not Applicable
statistical-table-shells	
4232-sec-16-2-6-individual-efficacy-response-data-statistical-	Not Applicable
table-shells	
4232-sec-16-2-7-adverse-event-listings-statistical-table-shells	
4232-sec-16-2-8-listing-individual-lab-measurements-statistical-	Not Applicable
table-shells	

Appendix B Good Specification Practice for Data Derivations

B.1 Sequence of ANELREA text:

The ANELREA text is prioritized in the following order:

- 1. "Unscheduled assessment"
- 2. "Assessment not planned"
- 3. "Record at baseline visit was excluded due to date after treatment start"
- 4. "Before in-trial observation period"
- 5. "After in-trial observation period"
- 6. "No measurement"
- 7. "Record was excluded due to subject being non-fasting"
- 8. "Retest rule 1: Not first value for visit"
- 9. "Assessment done after starting add on glucose lowering drug"

The ANELREA enters all BDS ADaM datasets.

CONFIDENTIAL

Date: Version: Status: Page:

Appendix C Table of converted units applied

Parameter	Topic code	SI unit	Conventional	Conversion factor
	*		unit	(SI to conventional
			(if required)	unit)
Total	T BILIRUBIN SERU	umol/L	mg/dL	0.058466
Bilirubin	M		-	
Creatinine	CREATININE_SERUM	umol/L	mg/dL	0.0113118
Fasting	FPG_PLASMA	mmol/L	mg/dL	18.02
Plasma				
Glucose				
HbA1c	HBA1C_BLOOD	%	mmol/mol	<src>*10.93-23.5</src>
HDL	HDL_CHOL_SERUM	mmol/L	mg/dL	38.61
Cholesterol			_	
Haemoglobin	HAEMOGLOBIN BLO	mmol/L	g/dL	1.6125
-	OD		_	
LDL	LDL CHOL SERUM	mmol/L	mg/dL	38.61
Cholesterol			_	
Calculated	CALC LDL CHOL SE	mmol/L	mg/dL	38.61
LDL	RUM			
Cholesterol				
Potassium	POTASSIUM_SERUM	mmolL	mEq/L	1
Total	T CHOL SERUM	mmol/L	mg/dL	38.61
Cholesterol			_	
Triglycerides	TRIGLYCERIDES_SE	mmol/L	mg/dL	89
	RUM		_	

Statistical Program. Specification		Date:	10 September 2019	Novo Nordisk
Trial ID: NN2211-4232	CONFIDENTIAL	Version:	1.0	
UTN: U1111-1170-7035	CONFIDENTIAL	Status:	Final	
EudraCT No: 2015-002417-29		Page:	42 of 42	

10 Change Log

Edition no.	1.0	Effective date:	10 Jun 2019
Changes to document	First version.		
	2.0	Effective date:	13 September 2019
	Trial specific updates
